6.2 BLINDING

Blinding refers to the assessment of outcome data without knowledge of baseline characteristics or treatment details. Results of neuroimaging will be assessed in a blinded manner, except for symptomatic side. Information on outcome at three months will be assessed as part of routine care.

6.3 STUDY PROCEDURES

BASELINE DATA OBTAINED AT ADMISSION

Clinical data, neuro-imaging data, data that might be related to treatment effect or to adverse events caused by the intervention, as well as several stroke risk factors, will be recorded in order to illustrate the representativeness of the study population (Table 1.1).

INCLUSION AND REGISTRATION

The registry office will be notified when a new patient is entered into the web-based database. Personal data will be sent to the registry office separately, through scrambled email.

FOLLOW-UP DATA

NIHSS scores at baseline and after 24-48 hours will be scored constructed from clinical data when missing. All patients will undergo CT or MR imaging at 2 days, if clinically indicated. Raw data will be forwarded to the trial office for blind evaluation. When there was no three month follow-up to determine mRS at three months, mRS score will be derived of discharge data or data from closed follow-up at another moment.²⁴

WITHDRAWAL

Patients can stop compliance with the registry at any time for any reason if they wish to do so without any consequences. **Every attempt will be made to complete follow-up in these patients. All patient data will be stored without identifying parameters.**

7. SAFETY REPORTING

7.1 SERIOUS ADVERSE EVENTS

A serious adverse event is any untoward medical occurrence or effect that can cause mortality, is life-threatening, requires prolonged hospitalization, or results in persistent significant disability.

Expected serious adverse events are neurologic deterioration, symptomatic intracranial hemorrhage, extracranial hemorrhage, technical complications or vascular damage at the target lesion such as perforation or dissection and mortality in the first week of stroke, aspiration pneumonia, and death from any cause until assessment of the 90-day follow-up.

A cumulative log will be kept of all serious adverse events. The executive committee will publish summary reports every 6 months.

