6. METHODS

6.1 STUDY OUTCOMES

PRIMARY OUTCOME

The primary outcome is the score on the modified Rankin Scale at 90 days (Appendix 1).

SECONDARY OUTCOMES

IMAGING PARAMETERS

- Infarct size assessed by CT at 2 days, when available. This includes manual tracing of the infarct perimeter and semi-automated pixel thresholding.^{22, 23}
- Pre-treatment and post-treatment TICl-score assessed on DSA acquired intervention.

CLINICAL PARAMETERS

- NIHSS at 24-48 hours days or at discharge.

FUNCTIONAL OUTCOME

Functional outcome will be assessed by means of the modified Rankin Scale at 90 days, this is done routinely in our centers, as standard of care.

SAFETY PARAMETERS

Safety is an issue of concern, as the experience with the intervention, overall, and within the participating centers, is limited. Safety parameters include hemorrhagic complications, and short-term outcome (mortality, NIHSS at 24-48 hours). As we will make use of web-based data-entry, these data will be available on short notice.

The primary safety parameter will be neurologic deterioration within 24 hours from inclusion in the registry. Neurological deterioration is defined as any decline in NIHSS of 4 points or more. In these patients, urgent brain CT is mandatory. This serious adverse event will be further classified as due to intracranial hemorrhage, ischemia or other (undetermined) cause. A full list of serious adverse events is provided in Appendix 5.

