5. ADVERSE EVENTS

1. Neurological deterioration
2. Symptomatic intracranial hemorrhage
3. Extracranial hemorrhage requiring surgery or blood transfusion

4. Technical complications at the target lesion such as perforation or dissection
5. Aspiration pneumonia and other infections, deep venous thrombosis and pulmonary embolism
6. Allergic reaction towards contrast fluid
7. Death from any cause within the registry period

An adverse event is considered serious when it causes mortality, is life-threatening, requires prolonged hospitalization, or results in persistent significant disability.

AMENDMENTS

AMENDMENT NO 1

February 15, 2016

Whole protocol: Barthel index and EQ5D are deleted from this protocol and not done in the Registry. Therefore every mention of this scores was deleted.

Page 1 the subtitle: "A multicenter registry of intra-arterial treatment for acute anterior circulation ischemic stroke" was changed into:

"A multicenter registry of intra-arterial treatment for circulation ischemic stroke"

At 'Authors' [name] was added.

Page 4: we replaced of 'Rational and aim' the first paragraph "After the last inclusion in the MR CLEAN trial there is a momentum in intra-arterial treatment for acute anterior circulation ischemic stroke in the Netherlands. The international guidelines and recommendations allow intra-arterial treatment as a rescue treatment, but proof of a beneficial effect of intra-arterial treatment on functional outcome is not available. New approaches to treatment that make use of stent-retrievers however, show promising results. Until the results of trials that make use of these stent-retrievers are known, clinicians will be inclined to use these devices on selected patients, especially on those that do not respond to or have contraindications for treatment with intravenous thrombolytics." with:

"After the last inclusion in the MR CLEAN trial there is a momentum in intra-arterial treatment for acute anterior circulation ischemic stroke in the Netherlands. The international guidelines and recommendations allowed intra-arterial treatment as a rescue treatment, but since early 2015, proof of a beneficial effect of intra-arterial treatment on functional outcome is available.¹⁴⁻¹⁸"

Furthermore on this page in the section 'study population' we changed "anterior circulation stroke" in "acute ischemic stroke" in both the first and last sentence.

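### The definition of a serious adverse event has no limb for a new hospital admission, so non-fatal events after discharge can be under-counted

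*Protocol*

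**What the plan says.** Seriousness is defined in two places in the protocol. Section 7.1 has "any untoward medical occurrence or effect that can cause mortality, is life-threatening, requires prolonged hospitalization, or results in persistent significant disability". Appendix 5 closes with "An adverse event is considered serious when it causes mortality, is life-threatening, requires prolonged hospitalization, or results in persistent significant disability". The hospital-stay limb is the same in both. The mortality limb differs: 7.1 asks whether the event could cause death, Appendix 5 whether it did.

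The protocol also names event types. In 7.1: "Expected serious adverse events are neurologic deterioration, symptomatic intracranial hemorrhage, extracranial hemorrhage", followed by technical complications, aspiration pneumonia and death. Section 6.1 states: "A full list of serious adverse events is provided in Appendix 5". That appendix is headed as a list of adverse events and includes "Aspiration pneumonia and other infections, deep venous thrombosis and pulmonary embolism".

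The only late time limit in 7.1 belongs to mortality: "death from any cause until assessment of the 90-day follow-up". Table 1.2 lists serious adverse events under follow-up without a window. The rule decides what enters the cumulative log in 7.1 and the summary reports published every 6 months. Section 2 makes safety an objective, together with associations of baseline parameters with adverse events.

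**The concern.** A patient who goes home and comes back with a non-fatal complication starts a new stay and does not extend an old one. The protocol expects discharge before the 90-day assessment, since section 6.3 allows the modified Rankin score to be derived from discharge data when there is no three-month follow-up. If the definition reaches such an event only when the patient happens still to be an inpatient, classification depends partly on when the patient left hospital and not only on what happened.

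Two things are at stake. The log and the six-monthly reports could omit some non-fatal events after discharge. And because length of stay plausibly varies with stroke severity and local practice, the omission need not be even across patients, which could disturb the associations with adverse events named in section 2.

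**Working it through.** The protocol states no figure to reproduce, so the check is a reading of the definitions against one test event. Take a complication that is non-fatal, not life-threatening and leaves no persistent disability.

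**Step 1: the hospital-stay limb.** The wording "is life-threatening, requires prolonged hospitalization, or results in persistent significant disability" allows two readings of a prolonged hospitalization: the current stay is extended, or a long stay of any kind is needed.

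| Situation | Reading 1: current stay extended | Reading 2: long stay of any kind |
|---|---|---|
| Still in hospital, stay extended | met | met if the stay counts as long; no threshold given |
| Discharged, short readmission | not met | not met |
| Discharged, long readmission | not met | met; no threshold given |

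The short readmission fails on both readings. The long readmission depends on the reading.

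**Step 2: the other limbs.** Life-threatening and disabling are excluded by the choice of test event. On mortality, Appendix 5 excludes the event because it did not cause death. Section 7.1, with "any untoward medical occurrence or effect that can cause mortality", may include it, but only by a judgement for which no criterion is given. Two centers could classify the same readmission differently and both follow the protocol.

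**Step 3: the named events.** Extracranial hemorrhage and aspiration pneumonia are named as expected serious events in 7.1 with no hospital-stay condition, so they are likely to be logged wherever the patient is. Other infections, deep venous thrombosis and pulmonary embolism appear only in Appendix 5. Two readings of that list are open:

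- Listed events are serious in themselves, as section 6.1 suggests. The loss is then mainly confined to unlisted events that are neither life-threatening nor disabling.
- The closing sentence filters the list. It speaks of an adverse event being considered serious under conditions, and the list carries the heading of adverse events, so this is the more natural reading. A short readmission for a deep venous thrombosis or a non-respiratory infection must then still pass the criteria, and it fails the hospital-stay limb.

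The protocol does not say which applies.

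**Step 4: what is untouched.** Deaths count regardless of hospital stay. The 90-day modified Rankin Scale does not use the rule. The primary safety parameter in section 6.1, an NIHSS decline of 4 points or more within 24 hours, does not use it either. The sample size of 500 has no serious-event input.

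**Step 5: size.** The protocol gives no readmission rate, non-fatal serious-event rate or length of stay, so no under-count can be calculated. An upper bound can be shown only on assumptions: if 350 to 425 of 500 patients are discharged alive and 5% to 15% of them have a non-fatal event leading to admission before day 90, then 350 × 0.05 = 17.5 and 425 × 0.15 = 63.75, or about 18 to 64 patients. This counts every such admission, including those that the list or another limb would catch. It is a ceiling under assumed inputs, not an estimate of lost events.

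**The case against.** The strongest reply is that the protocol names most of the likely causes of readmission. Section 6.1 calls Appendix 5 the full list of serious events, and that list contains infections, deep venous thrombosis and pulmonary embolism; 7.1 adds a broad mortality limb. On that view little is lost. This stands as a limit on the size. It does not remove the gap, because whether the closing sentence of Appendix 5 filters the list is unsettled and the two mortality limbs disagree.

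Three stronger conclusions are tempting, and the documents do not support them.

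- A reader might infer that serious events up to day 90 are in fact under-counted. Day 90 is tied to death only, and no window is stated for non-fatal events.
- A reader might infer a downward bias for everything after discharge. Deaths and life-threatening or disabling events count wherever they occur.
- A reader might infer distorted comparisons between centers. Section 8 plans none. An effect on the baseline associations in section 2 is possible but cannot be shown from the protocol.

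It can also be said that collecting admissions at 90 days is new work, since Table 1.2 lists only the modified Rankin Scale at that visit. That is correct and belongs in the cost.

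**Conclusion.** The gap is real and lies in the current text of both definitions. A short new admission for a non-fatal, non-life-threatening, non-disabling event does not meet the hospital-stay limb on either reading, while the same event can meet it by extending an inpatient stay. Non-fatal serious events after discharge can therefore be under-counted, possibly in relation to length of stay. This is a risk of unknown size, not an established bias. It is smallest if Appendix 5 events are serious in themselves and larger if the closing sentence filters them. The link to length of stay rests on the assumption that discharge timing varies with severity or local practice, on which the protocol gives no data. The main outcome and the primary safety parameter do not depend on this rule. The wording should be corrected, because safety is a stated objective and the rule determines what is logged and published.

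**What to change.** In section 7.1 and Appendix 5:

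1. Replace the hospital-stay limb with *requires hospital admission or prolongs an existing hospital stay*.
2. Use the same mortality wording in both places.
3. State whether events listed in Appendix 5 are serious in themselves or only if they meet the criteria, and align the sentence in section 6.1 with that choice.
4. State the collection window for non-fatal serious events.

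This changes a reporting definition and no patient's treatment. The text edits are small. The reported count of serious events will be somewhat higher, and counts logged before and after the change will not be directly comparable unless earlier entries are reclassified. One question on hospital admissions has to be added at three months. The Summary already plans an interview of all patients then, but the question is a new data item. Where the modified Rankin score is taken from discharge data because there was no three-month follow-up, admissions would stay unknown and should be recorded as such.

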8. STATISTICAL ANALYSES

Baseline characteristics and outcomes will be summarized by means of simple descriptive statistics. The main analysis of this study concerns the primary outcome at 90 days. Associations between baseline demographic and clinical characteristics and intervention details with the primary and secondary outcome will be analyzed. Associations are defined as the relative risk for improvement on the mRs and estimated as an odds ratio with ordinal logistic regression taking the whole range of the modified Rankin Scale (mRS) into account.²⁵ Similar associations of demographic and clinical characteristics and intervention details with secondary outcomes will be analyzed with standard statistical tests and multiple regression models to adjust for other prognostic factors.

9. ETHICAL CONSIDERATIONS, ACCESS TO APPROPRIATE TREATMENT

All patients will receive best medical treatment according to national and local guidelines and current insights. The decision to carry out the intervention will be made the local stroke team and investigators. The steering committee will issue recommendations with regard to treatment and medical management of the patients in the registry.

9.1 REGULATION STATEMENT

The registry will be conducted in accordance with the principles of the Declaration of Helsinki, as amended by the World Medical Association General Assembly in October 2008, and with the guidelines for Good Clinical Practice.

9.2 RECRUITMENT AND CONSENT

All patients will be provided with a written explanation of the study. The patients or their representatives will be given the opportunity to refuse participation. In that case all data will be deleted from the database and clinical material will be destroyed.

This registry makes use of “waste material” only, such as blood aspirated during intervention and retrieved thrombi. No additional blood will be drawn. However, substudies may require additional activities, for which separate written informed consent will have to be obtained.

Data of patients who died before they were asked for consent and data of patients who were recruited retrospectively since April 2014 will be entered anonymously in the study base. Patient material and data will be stored anonymously.

The study physician will inform the patient orally and in writing. In case the patient is legally incompetent, for example because of aphasia or anosognosia, the information will be given to a legal representative. Because the study physicians are also involved in the clinical care of patients with acute ischemic stroke, it appears inevitable that in some occasions the study physician and treating physician will be the same person.

9.3 BURDENS TO THE PATIENT

All patients will undergo an additional CT scan after 2 days to assess infarct size, if clinically indicated. Radiation exposure for this CT scan is 2.1-2.3 mSV (milliSievert).²⁶

Patients may be asked to participate in substudies (see section 10.2). Also, during the intervention aspirated blood may be kept and stored, as well as the thrombo-embolic material which is retrieved from the retraction devices (THRAPS substudy).

10. ADMINISTRATIVE ASPECTS AND PUBLICATION

10.1 PRIVACY

All included patients will be assigned a unique number. Name and address will be stored separately from the study data. The study physician will inform the patient orally and in writing. The information describes the purpose of the study, interventions, potential hazards and benefits and the procedures for recording of clinical information and three month follow up.

10.2 SUBSTUDIES

Within the framework of the MR CLEAN-R, several observational substudies are carried out. They were also active within the framework of the MR CLEAN trial itself. They will be summarized below. For each substudy the patients' written consent will be asked. For a full description of the study procedures see the appendices with study protocols.

THRAPS

THRAPS is an observational study of the thrombo-emboli and aspirate blood (waste material) that is retrieved during the intervention. We will relate histopathologic parameters with the effect of the procedure (recanalization, no reflow and functional recovery).

CLOT-MR CLEAN

The CLOT-MR CLEAN is a study on long term follow-up and cost-effectiveness of endovascular treatment for acute ischemic stroke. During a two-year period data on costs as well as clinical outcome will be assessed. The primary outcome parameters are the costs per patient without poor outcome on the modified Rankin Scale (mRS) and the costs per quality-adjusted life year (QALY). For the long-term clinical effect of endovascular treatment the mRs will be used as well as occurrence of recurrent strokes and mortality.

10.3 PUBLICATION POLICY

The writing committee for the main publication consists of members of the executive committee. Publication of the main study results, substudies described in this protocol and of future substudies will

be on behalf of the MR CLEAN-R investigators. All investigators will have the opportunity to read and comment on a manuscript before it will be submitted for publication.

12. TABLES

1.1 Baseline characteristics	
Demographics	Age, gender
Clinical	NIHSS, NIHSS supplemental motor score, pre-stroke mRs, blood pressure, GCS, weight, height, body temperature.
Medical history	Previous stroke, previous MI, PAD, diabetes mellitus
Medication	Antiplatelet agents, coumarines, heparin(oids), oral thrombin antagonists and

	oral factor Xa inhibitors., statines
Vascular risk factors	Hypertension, atrial fibrillation, diabetes mellitus, smoking, hypercholesterolemia
Laboratory parameters	INR, kreatinine, GFR (Cockcroft-Gault), serum glucose, CRP.
Neuroimaging	Thin slice and standard unenhanced: location, ASPECTS score, hemorrhagic transformation (NINDS/ECASS classification), hyperdense artery sign.
Treatment	Intended mode of endovascular treatment

1. STUDY PARAMETERS

1.2 Follow-up	
Treatment	Pre- and post intervention TICI-score, duration of procedure, actual mode of treatment
Clinical assessment at 24-48 hours	Clinical status, NIH Stroke Scale, NIHS supplemental motor scale
Neuro-imaging at 2 days (if clinically indicated)	Plain CT: location, ASPECTS score, hemorrhagic transformation (NINDS/ECASS classification), hyperdense artery sign.
Clinical assessment at 90 days	Modified Rankin Scale
Serious adverse events	See appendix 5

13. APPENDICES

1. MODIFIED RANKIN SCALE (MRS)

Category	Short description	Long description
0	No symptoms	No symptoms
1	Symptoms, no Disability	Minor symptoms that do not interfere with lifestyle
2	Slight disability	Slight disability, symptoms that lead to some restriction in lifestyle, but do not interfere with the patient's capacity to look after himself.
3	Moderate disability	Moderate disability, symptoms that significantly restrict lifestyle and prevent totally independent existence
4	Moderately severe disability	Moderately severe disability, symptoms that clearly prevent independent existence though not needing constant attention
5	Severe disability	Severe disability, totally dependent patient requiring constant attention day and night.
6	Dead	Death

5. ADVERSE EVENTS

1. Neurological deterioration
2. Symptomatic intracranial hemorrhage
3. Extracranial hemorrhage requiring surgery or blood transfusion

4. Technical complications at the target lesion such as perforation or dissection
5. Aspiration pneumonia and other infections, deep venous thrombosis and pulmonary embolism
6. Allergic reaction towards contrast fluid
7. Death from any cause within the registry period

An adverse event is considered serious when it causes mortality, is life-threatening, requires prolonged hospitalization, or results in persistent significant disability.

AMENDMENTS

AMENDMENT NO 1

February 15, 2016

Whole protocol: Barthel index and EQ5D are deleted from this protocol and not done in the Registry. Therefore every mention of this scores was deleted.

Page 1 the subtitle: "A multicenter registry of intra-arterial treatment for acute anterior circulation ischemic stroke" was changed into:

"A multicenter registry of intra-arterial treatment for circulation ischemic stroke"

At 'Authors' [name] was added.

Page 4: we replaced of 'Rational and aim' the first paragraph "After the last inclusion in the MR CLEAN trial there is a momentum in intra-arterial treatment for acute anterior circulation ischemic stroke in the Netherlands. The international guidelines and recommendations allow intra-arterial treatment as a rescue treatment, but proof of a beneficial effect of intra-arterial treatment on functional outcome is not available. New approaches to treatment that make use of stent-retrievers however, show promising results. Until the results of trials that make use of these stent-retrievers are known, clinicians will be inclined to use these devices on selected patients, especially on those that do not respond to or have contraindications for treatment with intravenous thrombolytics." with:

"After the last inclusion in the MR CLEAN trial there is a momentum in intra-arterial treatment for acute anterior circulation ischemic stroke in the Netherlands. The international guidelines and recommendations allowed intra-arterial treatment as a rescue treatment, but since early 2015, proof of a beneficial effect of intra-arterial treatment on functional outcome is available.¹⁴⁻¹⁸"

Furthermore on this page in the section 'study population' we changed "anterior circulation stroke" in "acute ischemic stroke" in both the first and last sentence.

Furthermore on this page under section 'intervention' we changed the second sentence of this paragraph by deleting "or stenting" and adding: ",including use of a retrievable stent"

Page 5: in the 'burden and risks associated with participation' we deleted "telephone" in the second sentence.

Furthermore in the ‘discussion section’ we changed the paragraph:

“MR CLEAN-R is a post-trial registry of the MR CLEAN trial. Enrollment will start soon after the last inclusion in the MR CLEAN trial (March 17 2014) until the eventual start of the next randomized controlled trial. Estimated enrollment period will be April 2014 to April 2016. The expected number of registered patients is at least 500.” into:

““MR CLEAN-R is a post-trial registry of the MR CLEAN trial. Enrollment will start soon after the last inclusion in the MR CLEAN trial (March 17 2014) at least until the eventual start of the next randomized controlled trials. Estimated enrollment period will be April 2014 to at least April 2016. The expected number of registered patients is at least 500.””

Page 6: the second paragraph of section ‘1.1 general introduction’ the seconde sentence “anterior circulation” was deleted.

the text of section ‘1.2 Effectiveness and safety of intra-arterial treatment trials’ was completely replaced by:

“After the last inclusion in the MR CLEAN trial and the start of this Registry there was a momentum in intra-arterial treatment for acute anterior circulation ischemic stroke in the Netherlands. The international guidelines and recommendations allowed intra-arterial treatment as a rescue treatment. During inclusion of patients in this Registry, since early 2015, proof of a beneficial effect of intra-arterial treatment on functional outcome has become available.¹⁴⁻¹⁸ Since then guidelines worldwide have been updated, recommending intra-arterial treatment with stent retrievers as standard therapy in patients with neuro-imaging –confirmed intracranial large vessel occlusion confirmed.^{19, 20”}

Page 6: in the section ‘1.3 Rationale: need for a registry of intra-arterial treatment’ the first paragraph was deleted. In the second paragraph “anterior circulation” was deleted.

Page 7, section ‘2.objectives’ we chanced the last sentence: “To identify associations of baseline clinical parameters with outcome and adverse events.” Into:

“To identify associations of baseline clinical and neuro-imaging parameters with outcome and adverse events.”

Furthermore we replaced the text of section 3 “This a prospective collected multicenter registry. At least 10 large hospitals will register patients over a period of at most two years, starting in April 2014. For the period of April 2014 through December 2014, data of prospectively registered patients in this period, and of patients who died before consent could be given will be entered retrospectively into the database. Actual prospective enrollment will start in January 2015.” with:

“This a prospective multicenter registry. At least 17 large hospitals will register patients over a period of at least two years, starting in April 2014. Data of prospectively registered patients after this date, and of patients who died will be entered retrospectively into the database. Actual prospective enrollment will start in January 2015.”

Section ‘4.1 patients’ we changed the first paragraph: “All patients with acute ischemic stroke of the anterior circulation who are treated intra-arterial treatment will be registered and followed.” Into:

“All patients with acute ischemic stroke of the anterior or posterior circulation who are treated intra-arterial treatment will be registered and followed. Patients who have been included in Randomized Clinical trials will be registered but not data on intervention, clinical and long term follow-up will be entered into the database, in order to maintain the blind.”

Page 8: in section ‘4.2 Registry inclusion and exclusion criteria’ we added the following sentence as begin: “All patients who underwent IAT for acute ischemic stroke will be registered. We will create a core dataset of patients who conform to specific in- and exclusion criteria, similar to the MR CLEAN trial criteria.”

We added the following to the inclusion criterion under section 4.2

- The patient was treated in a MR CLEAN center (list in appendix).

We added the following under exclusion from core data set, under section 4.2:

- Treatment in a non-MR CLEAN center.

Section ‘4.3 participating centers and center eligibility’ the total text was deleted and replaced by:

“All centers that have participated in the MR CLEAN trial now participate in the MR CLEAN registry.

As the purpose of the registry is to include all patients had intra-arterial treatment since closure of the MR CLEAN trial, we will also register patients treated in other centers (appendix). These patients will be entered into the extended registry, while we are awaiting a formal procedure for recognition and certification of stroke-intervention centers.”

Page 10: the section ‘Functional outcome’ was deleted and replaced by:

“Functional outcome will be assessed by means of the modified Rankin Scale at 90 days, this is done routinely in our centers, as standard of care.”

At section ‘6.2 Blinding’ the following changes were made:

Second sentence was deleted and the following sentence was added at the end:

“Information on outcome at three months will be assessed as part of routine care.”

Page 11: section ‘Follow-up data’ the next changes were made to the first paragraph:

Following sentence was added at the beginning: “NIHSS scores at baseline and after 24-48 hours will be scored constructed from clinical data when missing.”

And the last sentence was deleted and replaced by:

“When there was no three month follow-up to determine mRS at three months, mRS score will be derived of discharge data or data from closed follow-up at another moment.”

The second paragraph was deleted.

Page 12: The first paragraph on “recruitment and consent” (9.2) which reads as follows:

“Written informed consent will be obtained from all patients who have been prospectively recruited and a copy will be retained by the including centre and forwarded to the central trial office. All patients will be provided with a written explanation of the study. Because the treatment decision will be a clinical one informed consent for study participation and follow-up will be asked within 48 hours, before any study activity is undertaken. Any material (blood) and information that is taken from a patient who does not give consent for participation will be destroyed. This procedure has the advantage that no avoidable delays occur prior to the intervention.”

Was replaced with:

“All patients will be provided with a written explanation of the study. The patients or their representatives will be given the opportunity to refuse participation. In that case all data will be deleted from the database and clinical material will be destroyed.

This registry makes use of “waste material” only, such as blood aspirated during intervention and retrieved thrombi. No additional blood will be drawn. However, substudies may require additional activities, for which separate written informed consent will have to be obtained.”

We replaced the following sentence “Data of patients who died before they were asked for consent and data of patients who were recruited in the period April to December 2014 will be entered anonymously in the study base. “ with:

“Data of patients who died before they could be provided with information about the study and data of patients who were recruited retrospectively since April 2014 will be entered anonymously in the study base. Patient material and data will be stored anonymously.”

The first sentence of the last paragraph of section 9.2 is not applicable anymore and therefore the following text was deleted:

“After approval by the patient or his/her legal representative, the patient’s treating physician will inform a study physician of the presence of a patient with acute ischemic stroke who is potentially eligible for the present study.”

The following part of the last paragraph of 9.2 which reads:

“The study physician will inform the patient orally and in writing and will obtain his/her written informed consent. In case the patient is legally incompetent, for example because of aphasia or anosognosia, written informed consent will be obtained from a legal representative. Because the study physicians are also involved in the clinical care of patients with acute ischemic stroke, it appears inevitable that in some occasions the study physician and treating physician will be the same person.”,

was replaced by:

“The study physician will inform the patient orally and in writing. In case the patient is legally incompetent, for example because of aphasia or anosognosia, the information will be given to a legal representative. Because the study physicians are also involved in the clinical care of patients with acute

ischemic stroke, it appears inevitable that in some occasions the study physician and treating physician will be the same person.”

Page 13: the second sentence in “privacy” (9.2) which reads as follows:

“Consent with participation in the study will be asked from all patients after presenting them with standard written forms.”

Was replaced with:

“The study physician will inform the patient orally and in writing.”

